- Interim monitoring boundaries for efficacy or harm (section 10)
- Futility analyses (sections 10.2 and 10.4)
- Listings of grade 3 and 4 adverse events, serious adverse events (SAE), clinical organ failure and serious infections (PSEE), unanticipated problems (UP), suspected unexpected serious adverse reactions (SUSAR), and deaths.

Data reports will follow a similar format for all investigational agents. Each agent will have a small assigned team of unblinded statisticians, with 2-3 alternating teams when 2 or more agents are investigated in parallel. The unblinded statistician teams will cooperate in designing the master layout for the data reports and will serve as each other's backup when needed. The unblinded statisticians will be unblinded to several investigational agents in the platform trial; those for which they serve as primary statisticians, and those for which they serve as backup or advisory statisticians.

3 Analysis Principles

Each investigational agent versus control will be treated as a separate clinical trial; data reports will be for one "target" investigational agent and its corresponding randomized (pooled) control group. Investigational agents will not be directly compared against each other, unless explicitly stated in the agent-specific data analysis plan and agreed upon by all stakeholders. Therefore, in the event that several investigational agents are included in the platform trial in parallel, the pairwise comparisons of each agent versus control will **not** be adjusted for potential inflation of Type I error "due to multiple comparisons".

Comparisons will be of each investigational treatment against its (pooled) control arm.

Analysis populations:

- Comparisons for safety outcomes will be by modified intention-to-treat (mITT). The mITT analysis is restricted to participants who received a complete or partial infusion of the investigational agent/placebo; participants who did not receive any of the investigational agent/placebo are excluded.
- Comparisons for efficacy endpoints will be by intention-to-treat (ITT), unless otherwise stated. If analyses are by ITT, sensitivity analyses by mITT will be carried out for primary outcomes and key secondary outcomes.

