infection or death, is 5 days or 28 days. The **administrative censoring date** is the earlier of the cut-date of the dataset, or randomization date plus analysis time period.

Comment: The notion of "administrative censoring" is important in time-to-event analyses in the presence of competing risks. For example, the Fine-Gray method for estimating the sub-hazard ratio for sustained recovery can be approximated by using a Cox proportional hazards model where follow-up time for participants who died prior to achieving sustained recovery is not censored at death, but at the administrative censoring date.

Censoring for time-to-event analyses

For interim analyses, the type of censoring used will depend on the data collection schedule.

- If the reporting of the endpoint is data-driven (e.g., SAEs and deaths are reported as they occur), then follow-up is censored at the administrative censoring date, at the date of withdrawal, or loss to follow-up, whichever occurs earliest.
- If the date of the event is elicited retrospectively at fixed study visits spaced more than one week apart (e.g., "sustained recovery"), follow-up will be censored at the last day the endpoint status was ascertained.
- Sensitivity analyses will be provided for key analyses when the outcome status is uncertain.

For **final** analyses, follow-up will be censored on the last day the outcome status was ascertained.

Adverse events (AEs) will be classified by system organ class according to MedDRA®¹ (currently version 24.1 [September 2021] is used; when new versions are implemented, items are recoded). AEs will be graded according to the *DAIDS Table for Grading the Severity of Adult and Pediatric Adverse Events, Corrected Version 2.1 (July 2017)* (also referred to as the *DAIDS AE Grading Table*).⁷ Cause of death will also be coded according to MedDRA®.

The number and percent of participants with grade 1-4 AEs will be summarized by day and grade, and by MedDRA® System Organ Class and grade. The percentage of participants with AEs will be compared between treatment groups according to grade cut-offs, e.g., "percent of participants with any AE", "percent of participants with grade 2 or higher AEs", etc., using CMH tests. The total number of events and median (IQR) of events per participant will also be summarized.

Additionally, the incidence of grade 3 and higher AEs will be summarized (number and percent of participants), and compared between treatment groups using time-to-event methods.

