In order to streamline the reporting of events, it was decided that certain protocol-specified exempt events (PSEE) are *not reported as SAEs*, unless they are considered related to the study treatment by the investigator. The events are listed in Appendix B; their composite is referred to as *clinical organ failure or serious infections*. While the *clinical organ failure or serious infection* events are serious events like SAEs, these events are reported not on the SAE eCRF unless they are considered related to the study treatment, but are reported as study endpoints on various other eCRFs.

The following safety and tolerability outcomes will be analyzed. If sample size permits, models will be stratified by disease severity and study site pharmacy, as described in section 3 under "stratification", unless noted otherwise.

- The **primary safety endpoint** is a composite of incident grade 3 or 4 clinical adverse events, SAEs, clinical organ failure or serious infections, or death through **Day 5**. The number and proportion of participants experiencing one of these events up through Day 5 will be tabulated, and treatment groups will be compared using a CMH test stratified by study site pharmacy and by disease severity at study entry.
 - Mortality will be analyzed as a key secondary outcome, see below.
 - The individual components of the composite outcome will be summarized.
 - Sensitivity analyses: For interim analyses, while the trial is still enrolling, treatment groups will also be compared for time to event through Day 5 using a log-rank test, stratified by site pharmacy and disease severity at study entry; the HR will be estimated with a 95% CI using a Cox proportional hazards model, and the cumulative proportion of participants with events over the first 5 days in each treatment group will be estimated using Kaplan-Meier curves.

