 - Composite of incident grade 3 or 4 clinical adverse events, SAEs, clinical organ failure or serious infection, or death through Day 28
 - Components of the composite endpoint will be also be summarized, overall and by system organ class. Proportions of participants who experienced any of these events by Day 28 will be compared using stratified CMH tests or logistic regression.
 - Composite of SAEs, clinical organ failure, serious infection, or death through Day 28 and Day 90
 - Composite of hospital re-admission or death through 18 months
- Treatment groups will be compared for the incidence of non-pulmonary events in the pulmonary+ ordinal outcome that are not part of the pulmonary outcome, through Day 5 and Day 7 (using time-to-event methods, with death as competing risk). These events are shown in red in Appendix A.
- AEs, SAEs, and UPs will be classified by MedDRA® system organ class. AEs will be graded for severity according to the *DAIDS AE Grading Table*. Grade 1-4 clinical AEs will be reported at baseline (Day 0 prior to infusion of the investigational agent), Day 0 after the infusion, Days 1-7, and on Days 14 and 28.

The number and percent of participants with AEs will be summarized by day (Day 0 separately prior and after the infusion) and grade, and by system organ class and grade. Comparisons between treatment groups will be for the proportion of participants with AEs of a given grade or higher (i.e., any grade, grade 2+, grade 3+, grade 4). The treatment comparisons will be performed using stratified CMH tests or logistic regression.

- For comparisons by day, the proportion of participants with any grade AEs will be compared for Days 0 (after infusion) through 7, and on Days 14 and 28.
- For comparisons by grade, the proportion of participants who experienced any grade AEs (grade 2+ AEs, etc.) between Day 0 (after the infusion) through Day 7 will be compared.
- For the comparison by system organ class, CMH tests will be performed if the number of participants with AEs is sufficiently large. System organ classes may be split up into MedDRA® preferred terms (PT) for system organ classes where the treatment difference is significant.

Other clinically meaningful AE groupings (beyond system organ class) may be developed by the study team, who are blinded to the treatment effect.

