 In addition to any grade AEs through Day 7, grade 3 and 4 clinical AEs are being reported through Day 28. The number and percent of participants with incident grade 3 or 4 AEs through Day 28 will be summarized, overall and by system organ class, and compared between treatment groups using stratified CMH tests. (A grade 3 or 4 AE is considered "incident" if the event was not present at baseline or increased to grade 3 or 4 from grades 1 or 2.)

To illustrate the time course, the incidence of *grade 3 or 4 AEs or death* through Day 28 will be summarized by treatment group using Kaplan-Meier estimates of the cumulative incidence functions (CIF).

- Infusion-related reactions and symptoms during infusion or within 2 hours after infusion of the investigational agent or placebo, and infusion cessation prior to completion will be tabulated and compared between treatment groups; analyses are described in section 6.
- Treatment groups will be compared for the proportion of participants who developed *organ failure or serious infections* through Day 28 and through Day 90, overall and by individual components, using stratified CMH tests. Individual components of this composite outcome will be tabulated.
- Treatment groups will be compared for incidence of organ failure, serious infections, or death through Day 28 and through Day 90, using Cox proportional hazards models; cumulative incidence functions will be estimated using Kaplan-Meier estimates.
- Treatment groups will be compared for incidence of a composite of fatal and non-fatal cardiovascular and thromboembolic events, a subset of the organ failure outcome (items 6b1, 6e2, 6e3, and 6f2 in Appendix B). Treatment groups will be compared using Cox proportional hazards models; cumulative proportions of participants with such events will be estimated using Kaplan-Meier estimates.

Comment: Death for causes other than cardiovascular or thromboembolic events is a competing risk. As sensitivity analysis, the treatment groups will be compared using Aalen-Johansen estimates for the cumulative incidence functions and Fine-Gray models to estimate the sub-hazard ratio (investigational agent versus placebo) for the composite outcome. If results differ substantially from the Cox regression and Kaplan-Meier estimates, mortality for reasons other than CVD and thromboembolic events will be investigated in detail.

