 Treatment groups will be compared for new requirements of dialysis, overall and in subgroups by eGFR level (<30 mL/min versus 30 mL/min at study entry), and subgroups by nAb status at study entry (nAb negative or positive).

Motivation: In a joint analysis of data from the first three agents studied in TICO (bamlanivimab, sotrovimab, and BRII 196/198), the incidence of dialysis was elevated in the active treatment group compared with placebo (18 versus 2 events, HR=5.7 [95% CI: 1.2-24.6]). This safety signal was seen only among those who were nAb seronegative at study entry (16 events in the active arms versus 2 placebo, HR=5.0 [95% CI: 1.1 to 22.0]),

while only 2 events occurred among those who were nAb seropositive at study entry, both in the active arms. The mean time from enrollment to needing dialysis was 21 days.

Comment: Of the 20 participants with "incident dialysis", 2 had required dialysis prior to their COVID-19, and thus may be mis-classified for treatment-emergent dialysis. Both had eGFR < 10 mL/min at study entry and thus were at high risk for dialysis, and both had been allocated to active treatment.

Hypothesis: The incidence of dialysis is elevated with nMAb treatment compared with placebo, in particular among those with eGFR < 30 mL/min, and among those who are nAb seronegative at study entry.

- Treatment groups will be compared for mean changes in laboratory test values from baseline to Day 5, and for incidence of grade 3 and 4 laboratory abnormalities at Day 5 (new abnormality or increase in grade). Laboratory tests are conducted locally, and include serum creatinine, AST/SGOT or ALT/SGPT, WBC, hemoglobin, platelet counts, lymphocyte counts, and C-reactive protein. Statistical methods are described in section 3.
- Participants who are pregnant are not eligible for enrolment. For participants who become pregnant, pregnancy outcomes will be summarized.
- In addition to the safety outcomes specified in the platform protocol, other targeted safety outcomes for specific investigational agents may be specified in appendices to the protocol. Analyses will be specified in the corresponding agent-specific appendix to this SAP.

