Listings of SAEs, clinical organ failure and serious infections, incident grade 3 and 4 AEs, UPs, SUSARs, and deaths (with cause of death) by treatment group will be provided at each DSMB meeting, with new events highlighted. The listings will include important baseline characteristics, such as age, sex, and disease severity (pulmonary outcome category) at study entry.

Further safety assessments may be considered.

Corticosteroid use will be monitored; concomitant medication use is collected at baseline and at Day 5.

- Corticosteroid use (any use at baseline or Day 5) will be summarized by treatment group and by oxygen requirement (worst category through Day 5: no supplemental oxygen, < 4 L/min, conventional supplemental oxygen > 4 L/min, high-flow oxygen or mechanical ventilation/ECMO).
- Corticosteroid use on Day 5 will be summarized by treatment group and by oxygen requirement (worst category on Day 5, as above).

The impact of study arm on composite safety outcomes and their components at day 5, 28 and 90 will be assessed for subgroups defined by baseline characteristics, including SARS-CoV-2 antibody serostatus, antigen levels, demographics, duration of symptoms at enrollment, baseline classification of "home", clinical history and presentation (including disease severity stratum and pulmonary+ ordinal outcome at baseline). Tests for homogeneity of the treatment effect across subgroups will be carried out.

Outcomes and methods for subgroup analyses are described in detail in section 9.

8 Efficacy Analyses

Analysis cohort: Comparisons between each investigational agent and its concurrently randomized (pooled) controls will be by intention-to-treat (ITT) unless otherwise stated.

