10.1 Early Assessment of Safety

For investigational agents with minimal pre-existing data, the pace of enrollment will be initially restricted and the DSMB will be asked to review safety data for the first 20 to 30 participants before increasing the pace of enrollment.

Subsequently, the DSMB will carry out regular reviews of safety data reports. These reports will include summaries of infusion–related events, grade 1-4 AEs, SAEs, organ failure, serious infections, and deaths, including the primary safety outcome at Day 5, and Day 28. Event listings for incident grade 3 and 4 AEs, SAEs, organ failure and serious infections, SUSARs, UPs and deaths will be provided (events that were reported since the previous review will be marked). Narratives will be provided for selected SAEs, SUSARs or UPs, particularly those judged related to study treatment. Analyses are described in section 7.

Monitoring boundary for harm:

- Until the first 300 participants are enrolled (150 per study arm) and the early futility analysis is conducted, the treatment groups will also be compared for the "pulmonary" and "pulmonary+" ordinal outcomes at Day 5, using a proportional odds model stratified by study pharmacy and pulmonary+ outcome category at baseline. A Haybittle-Peto boundary with 2.5 standard deviation (SD) for the first 50 participants enrolled and 2.0 SD afterwards will be used as a guideline for harm.
- After the study population is expanded to include disease severity stratum 2, these analyses are performed by disease severity stratum.

At the discretion of the DSMB, these safety reports will be prepared at a frequency they specify, for example, weekly. The DSMB may also request additional data summaries.

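### The SAP's definition of an incident grade 3 or 4 clinical adverse event leaves out worsening from baseline grade 3 to grade 4, although its laboratory rule counts that step

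*SAP*

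**What the plan says.** SAP section 7 (Safety Analyses) defines the term where it describes grade 3 and 4 clinical events through Day 28. Such an event is incident "if the event was not present at baseline or increased to grade 3 or 4 from grades 1 or 2". The same section applies a different rule to laboratory values, comparing the arms for "incidence of grade 3 and 4 laboratory abnormalities at Day 5 (new abnormality or increase in grade").

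The clinical term is used in these places:

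- **Primary safety endpoint, section 7:** "a composite of incident grade 3 or 4 clinical adverse events, SAEs, clinical organ failure or serious infections, or death through" Day 5.
- **Day 28 endpoint, section 7:** "Composite of incident grade 3 or 4 clinical adverse events, SAEs, clinical organ failure or serious infection, or death through Day 28".
- **Comparison of incident grade 3 or 4 events through Day 28, section 7:** stratified CMH tests.
- **Listings for each DSMB meeting, section 7:** these cover "incident grade 3 and 4 AEs, UPs, SUSARs, and deaths (with cause of death) by treatment group", among other items.
- **Safety reports, section 10.1:** "Event listings for incident grade 3 and 4 AEs, SAEs, organ failure and serious infections, SUSARs, UPs and deaths will be provided".

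The closed-report outline in section 2 does not restrict its listing to incident events: "Listings of grade 3 and 4 adverse events, serious adverse events (SAE), clinical organ failure and serious infections (PSEE" and further categories. Section 7 also provides for grade 1 to 4 clinical events to be recorded at baseline, before the infusion.

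**The concern.** The clinical definition is a closed list with two entries: absent at baseline, or risen from grade 1 or 2. A participant who enters with a grade 3 event that then becomes grade 4 fits neither, although grade 4 is the highest grade the SAP reports for adverse events. The laboratory rule counts the same step, and the SAP gives no reason for the difference.

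The term matters because it defines part of the primary safety endpoint. Section 7 describes the Day 5 composite as the main safety measure during enrolment for agents given as a single infusion. Participants are inpatients and baseline events are graded up to 4, so the plan itself allows for grade 3 events at entry. A programmer who follows the definition as written would leave out a real worsening.

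**Working it through.** The documents give no figure to reproduce, so the check applies both rules to every case.

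**Inputs.** Let b be the baseline grade (0 = absent, then 1 to 4) and f the follow-up grade (3 or 4). Both rules come from SAP section 7.

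- Clinical rule: incident if f is 3 or 4 and b is 0, 1 or 2.
- Laboratory rule: counted if f is 3 or 4 and either b = 0 or f > b.

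| Baseline b | Follow-up f | Clinical rule | Laboratory rule |
|---|---|---|---|
| 0 | 3 | yes | yes |
| 0 | 4 | yes | yes |
| 1 | 3 | yes | yes |
| 1 | 4 | yes | yes |
| 2 | 3 | yes | yes |
| 2 | 4 | yes | yes |
| 3 | 3 | no | no |
| **3** | **4** | **no** | **yes** |
| 4 | 3 | no | no |
| 4 | 4 | no | no |

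The clinical rule counts 6 of 10 combinations and the laboratory rule 7 of 10. The one difference, 7 − 6 = 1, is baseline grade 3 to follow-up grade 4.

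**Could the wording be read to include it?** One might take the event to be the grade 4 episode itself, so that it was not present at baseline. On that reading a rise from grade 1 or 2 would also be new, and the second clause would add nothing. The second clause has a purpose only if the event is the underlying condition whatever its grade, and then the 3-to-4 step is left out.

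**Where would a non-serious 3-to-4 worsening still appear?**

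| Place in the SAP | Captures it? |
|---|---|
| Comparison by grade, including grade 4, after infusion through Day 7 (section 7) | Yes; not limited to incident events |
| Summaries by day and grade (sections 3 and 7) | Yes, descriptively |
| Closed-report listing (section 2) | Yes |
| Day 5 and Day 28 composites (section 7) | No, unless it is also an SAE, organ failure, a serious infection or fatal |
| CMH comparison through Day 28 (section 7) | No |
| Listings of incident events (sections 7 and 10.1) | Not as a grade 3 or 4 event |

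The event is therefore visible, but nothing returns it to the primary composite or the Day 28 comparison.

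**Size.** The number affected in each arm would be the number with a grade 3 event at baseline, times the proportion worsening to grade 4, times the proportion of those with no other component event. The documents give none of these three quantities, so no effect on the composites can be calculated.

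**The case against.** The strongest reply is that the gap is almost closed elsewhere. The unrestricted grade 4 comparison through Day 7 covers the whole Day 5 window. Appendix B places respiratory failure, vasopressor use, new renal replacement therapy, heart failure, major bleeding and thromboembolism under organ failure, so many serious deteriorations reach the composites whatever the baseline grade. What remains is a worsening that is not serious, not organ failure, not a serious infection and not fatal. Section 7 adds that the usual main safety results at publication are mortality and a Day 90 composite without grade 3 or 4 events. All of this stands and keeps the point small. It does not change what the primary endpoint counts.

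A second reply is that laboratory values and clinical events are different data and may have different rules. They may, but the SAP gives no reason for treating the 3-to-4 step differently. A third is that the supplied protocol is only Appendix H5, which refers adverse event assessment to section 10 of the master protocol. Whether that section also defines the term cannot be checked here. The SAP nevertheless states its own definition.

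Some stronger readings are tempting, but the documents do not support them:

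- **That these worsenings are hidden from the DSMB.** The section 2 listing and the summaries by grade show them.
- **That the rule favours one arm.** It applies equally to both blinded arms, and nothing points to a one-sided effect.
- **That other wording shows a second, conflicting definition.** Section 3 says "the incidence of grade 3 and higher AEs will be summarized (number and percent of participants), and compared between treatment groups using time-to-event methods", but incidence there need not mean a different scope. The composite named without the word incident in section 9 and Appendix G is most likely shorthand.
- **That the MP0420 rash summaries in Appendix G have a related defect because they are not split by onset.** Appendix G already reports rash with muscle, joint or general pain by arm and lists each event. A further split is a preference about a descriptive table.

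**Conclusion.** The point holds as a gap in a stated definition. Read literally, baseline grade 3 worsening to grade 4 is not counted in the adverse event component of the Day 5 primary safety composite or the Day 28 composite, in the CMH comparison through Day 28, or in the incident-event listings of sections 7 and 10.1. The laboratory rule in the same section would count it.

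The effect is probably small and cannot be computed from the documents. That judgement rests on the other routes into the composites and on an assumption that non-serious 3-to-4 worsening is uncommon, which the documents neither confirm nor contradict. It may be a drafting oversight. It should be corrected because it touches the primary safety endpoint and is cheap to correct, but it does not undermine the safety evaluation as a whole.

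**What to change.** In SAP section 7, define an incident grade 3 or 4 clinical adverse event as one that was not present at baseline, or that is at a higher grade than at baseline. State that this definition governs the Day 5 and Day 28 composites, the CMH comparison through Day 28, and the listings in sections 7 and 10.1. In the table under working, only the 3-to-4 row changes.

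The cost is one phrase and one derivation rule. Baseline grades are already recorded before infusion, so no new data are needed. Section 1.1 provides for SAP updates by blinded statisticians and clinical investigators before each agent is unblinded, so the change can be made as a prespecified clarification.
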